9 SAFETY ASSESSMENTS

Safety and tolerability assessments will include the monitoring of adverse events; AESIs (ie, pruritus [Part A only], drug-induced liver injury [Part A only], elevation of transaminases [Part B only], and all muscle-related adverse events); SAEs; and findings from physical examinations, vital signs, ECGs, and clinical laboratory parameters.

Throughout the study, all TEAEs, clinical assessments, and clinical laboratory parameters will be closely monitored against the criteria for drug-induced liver injury and muscle toxicity as detailed in the Clinical Safety Monitoring Plan ([Appendix E](#)).

All adverse events will be assessed and reported using the National Cancer Institute CTCAE Version 5.0 grading system. Additional safety measurements will be performed at the discretion of the Investigator (or delegate).

9.1 Adverse Events

An adverse event is defined as any untoward medical occurrence in a clinical investigation patient administered a pharmaceutical product, which does not necessarily have a causal relationship with this treatment. An adverse event can therefore be any unfavorable and/or unintended sign (including an abnormal laboratory finding), symptom, or disease temporally associated with the use of an investigational medicinal product, whether or not related to the investigational medicinal product. All adverse events, including observed or volunteered problems, complaints, or symptoms, are to be recorded on the appropriate eCRF.

Adverse events, which include clinical laboratory test variables, will be monitored and documented from the time of informed consent until the EOS Visit. Patients should be instructed to report any adverse event that they experience to the Investigator, whether or not they think the event is due to study drug. Beginning at the time of informed consent, Investigators should make an assessment for adverse events and record the event on the appropriate adverse event eCRF. Beginning with receipt of first dose of study drug, any adverse event that occurs during the Treatment Period will be recorded as a TEAE on the appropriate eCRF.

Wherever possible, a specific disease or syndrome rather than individual associated signs and symptoms should be identified by the Investigator and recorded on the eCRF. However, if an observed or reported sign or symptom is not considered a component of a specific disease or syndrome by the Investigator, it should be recorded as a separate adverse event on the eCRF. Additionally, the condition that led to a medical or surgical procedure (eg, surgery, endoscopy, tooth extraction, or transfusion) should be recorded as an adverse event, not the procedure itself.

Any medical condition already present at screening should be recorded as medical history and not be reported as an adverse event unless the medical condition or signs or symptoms present at baseline changes in severity, frequency, or seriousness at any time during the study. In this case, it should be reported as an adverse event: worsening of preexisting condition.

Clinically significant abnormal laboratory or other examination (eg, ECG) findings that are detected during the study or are present at screening and significantly worsen during the study should be reported as adverse events, as described below. The Investigator will exercise his or her medical and scientific judgment in deciding whether an abnormal laboratory finding or other abnormal assessment is clinically significant. Clinically significant abnormal laboratory values occurring during the clinical study will be followed until repeat tests return to normal, stabilize, or

are no longer clinically significant. Abnormal test results that are determined to be an error should not be reported as an adverse event. Laboratory abnormalities or other abnormal clinical findings (eg, ECG abnormalities) should be reported as an adverse event if any of the following are applicable:

- If an intervention is required as a result of the abnormality (such as a re-test being made more than 1 time)
- If action taken with the study drug is required as a result of the abnormality
- Based on the clinical judgment of the Investigator

9.1.1 Adverse (Drug) Reaction

All noxious and unintended responses to a medicinal product related to any dose should be considered an adverse drug reaction. “Responses” to a medicinal product means that a causal relationship between a medicinal product and an adverse event is at least a reasonable possibility, ie, the relationship cannot be ruled out.

9.1.2 Unexpected Adverse Drug Reaction

An Unexpected Adverse Drug Reaction is defined as an adverse reaction, the nature or severity of which is not consistent with the applicable product information. For EYP001a, the reference safety information is included in the Investigator’s Brochure currently in force. The reference safety information will be reviewed yearly and the periodicity of the review will be harmonized with the reporting period of the Development Safety Update Report.

9.1.3 Assessment of Adverse Events by the Investigator

The Investigator will assess all adverse events using the National Cancer Institute CTCAE Version 5.0 grading system.

Causality Assessment

The relationship of an adverse event to the administration of the study drug is to be assessed according to the following definitions:

- **Definite:** An adverse event that is consistent with the suspected type of reaction known for the drug, in line with the reasonable temporal order after treatment, and is alleviated or disappears upon discontinuation of the study drug.
- **Probable:** An adverse event that is consistent with the suspected type of reaction known for the drug, in line with the reasonable temporal order after treatment, alleviates or disappears upon discontinuation of the study drug, but could also be caused by the clinical conditions of the study patient or other factors.
- **Possible:** An adverse event that is consistent with the suspected type of reaction known for the drug, not in line with the reasonable temporal order after treatment, and could also be caused by the clinical conditions of the study patient or other factors.
- **Improbable:** An adverse event that is inconsistent with the suspected type of reaction known for the drug, not in line with the reasonable temporal order after treatment, and could also be caused by the clinical conditions of the study patient or other factors.

- Not related: An adverse event that is inconsistent with the suspected type of reaction known for the drug, not in line with the reasonable temporal order from administration of the study drug, or that can be easily explained by other factors, such as underlying diseases, complication, concomitant drugs, and concurrent treatment.

The following factors should also be considered:

- The temporal sequence from study drug administration-
 - The event should occur after the study drug is given. The length of time from study drug exposure to event should be evaluated in the clinical context of the event.
- Underlying, concomitant, intercurrent diseases-
 - Each report should be evaluated in the context of the natural history and course of the disease being treated and any other disease the patient may have.
- Concomitant drug-
 - The other drugs the patient is taking or the treatment the patient receives should be examined to determine whether any of them might be recognized to cause the event in question.
- Known response pattern for this class of study drug-
 - Clinical and/or preclinical data may indicate whether a particular response is likely to be a class effect.
- Exposure to physical and/or mental stresses-
 - The exposure to stress might induce adverse changes in the patient and provide a logical and better explanation for the event.
- The pharmacology and PK of the study drug-
 - The known pharmacologic properties (absorption, distribution, metabolism, and excretion) of the study drug should be considered.

See [Section 4.4](#) for withdrawal criteria.

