3.2 Stopping Rules

Dosing of a patient may be discontinued for any of the following events:

- One occurrence of an SAE assessed to be definitely or probably related to dosing with the study drug. See [Section 9.1.3](#).
- Confirmation of any of the study drug discontinuation criteria as described in the Clinical Safety Monitoring Plan ([Appendix E](#)).
- $CK \geq 5 \times ULN$.
- Signs/symptoms of acute coronary syndrome.
- Confirmed cardiac troponin I concentration increase (performed centrally) from baseline and $>ULN$.
- Occurrence of any condition that, in the opinion of the Investigator, significantly jeopardizes the wellbeing and safety of the patient and is assessed to be probably related to dosing with the study drug.
- Clinically significant changes in vital signs or ECGs (such as arrhythmias) or in the safety laboratory tests assessed to be probably (ie, no alternative explanation likely) related to dosing with the study drug. A “possible” relationship is not considered to require a suspension of treatment.

If 2 or more patients meet study drug stopping criteria, dosing should be suspended or terminated for the remaining patients. The DSMC must review all safety data and provide clearance prior to dosing any additional patients.

For clinical sites in the United Kingdom or European Union, in the case of study halt, the study may only be restarted after Medicines & Healthcare Products Regulatory Agency or National Competent Authority approval, respectively, via a substantial protocol amendment.

If a patient experiences a Grade 5 CTCAE toxicity, or if more than 2 patients develop a \geq Grade 3 CTCAE toxicity in the same category, the study will be paused and safety reports will be submitted to the DSMC for review and clearance prior to dosing any additional patients.

Reinitiation of study drug may be considered after consultation with the Medical Monitor.

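### Protocol 9.1.3 defines Possible by timing that does not fit the drug, so well-timed events without positive dechallenge, or of a new type, have no grade of Possible or higher

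*Protocol*

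**What the plan says.** Protocol 9.1.3 asks the investigator to grade relationship to study drug by five definitions:

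- **Definite:** known reaction type, "in line with the reasonable temporal order after treatment, and is alleviated or disappears upon discontinuation of the study drug".
- **Probable:** the event "alleviates or disappears upon discontinuation of the study drug, but could also be caused by the clinical conditions of the study patient or other factors"; the conditions on type and timing are the same as for Definite.
- **Possible:** "consistent with the suspected type of reaction known for the drug, not in line with the reasonable temporal order after treatment", with another cause conceivable.
- **Improbable:** "inconsistent with the suspected type of reaction known for the drug, not in line with the reasonable temporal order after treatment", with another cause conceivable.
- **Not related:** type inconsistent with the drug, "not in line with the reasonable temporal order from administration of the study drug, or that can be easily explained by other factors".

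A list of further factors follows, including temporal sequence, other diseases and drugs, class effect and pharmacology.

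Protocol 9.1.1 calls a response an adverse drug reaction when "a causal relationship between a medicinal product and an adverse event is at least a reasonable possibility, ie, the relationship cannot be ruled out". Protocol 9.1.2 provides for reactions that are unexpected in either nature or severity.

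The grades are used downstream. Protocol 3.2 lists, among the events for which a patient's dosing may be discontinued, "One occurrence of an SAE assessed to be definitely or probably related to dosing with the study drug". Protocol 10.2.4.1 and SAP 3.7.1 tabulate study drug-related TEAEs and serious events. Protocol 9.5 covers expedited reporting of SUSARs. Neither document says which of the five grades count as related.

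**The concern.** Possible and Improbable both require timing that does not fit; they differ only in whether the reaction type is known. No grade covers the ordinary middle case of an event whose timing fits, which the drug may have caused and something else may have caused too. The known-type condition on the top three grades also leaves no place for a new toxicity, which an early-phase trial exists partly to find.

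At stake are the drug-related subset of the safety tables and the investigator's opinion that enters the SUSAR assessment. An investigator who follows the definitions will tend to put such events in the lowest grades, or will find that none applies. One who does not follow them will use a private scale. With about 50 sites, both can happen, and the drug-related tables would then mix the two.

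**Working it through.** The protocol gives no figure to reproduce. The check is to read the definitions literally and see which events they can hold.

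**Attributes.** The definitions turn on four yes/no attributes: reaction type known for the drug, timing fits, improvement on stopping (positive dechallenge), and another conceivable cause. That makes 2 × 2 × 2 × 2 = 16 combinations. To separate Definite from Probable, Definite is taken to mean that no other cause is in play.

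| Combination | Number | Definite, Probable or Possible applies |
|---|---|---|
| Timing fits, known type, positive dechallenge | 2 | 2 |
| Timing fits, known type, no positive dechallenge | 2 | 0 |
| Timing fits, type not known | 4 | 0 |
| Timing does not fit, known type | 4 | 2 |
| Timing does not fit, type not known | 4 | 0 |
| All | 16 | 4 |

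With fitting timing, 2 of 8 reach one of the top three grades, and 8 − 2 = 6 do not. With a type not known for the drug, 0 of 4 + 4 = 8 do.

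**Not related.** Its wording is ambiguous. If any one of its three conditions suffices, 1 of the 16 combinations has no grade at all: known type, fitting timing, no positive dechallenge, no other cause. If type and timing must both fail, or other factors must explain the event, 5 of 16 have none. Both counts treat another conceivable cause as one that easily explains the event.

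**The order is reversed.** Take a known-type event, with no dechallenge and another conceivable cause. If its timing does not fit, it is Possible. If its timing does fit, Possible is barred, Definite and Probable fail for want of dechallenge, and only Not related can apply. Better timing lowers the grade.

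**Against 9.1.1 and 9.1.2.** A well-timed event with no dechallenge information can readily be one whose relationship to the drug remains open, which makes it a reaction under 9.1.1. Under 9.1.3 it cannot be Possible. A reaction unexpected in nature is foreseen by 9.1.2, but 9.1.3 gives it nothing above Improbable.

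**Cases in this trial.**

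- Investigators reported pruritus in 5 of 6, 3 of 5 and 5 of 6 patients in the three active groups of Part A (Protocol 1.2.2). Protocol 9.12.1 begins with topical measures, notes that tolerance may develop under continued dosing, and describes itch as a symptom of NASH itself. A patient who keeps dosing has known type, fitting timing, no dechallenge and another cause.
- For transaminase rises, Appendix E has repeat testing and close observation at levels below those that require discontinuation. Such an event can be graded while the drug continues.
- A fatal event cannot improve on stopping. If well timed, it is shut out of all three upper grades.

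**Against 3.2.** The SAE criterion depends on Definite and Probable, which themselves require improvement after the drug is stopped. A criterion for stopping therefore presupposes that stopping has happened. Section 3.2 also glosses a probable relationship, in its item on vital signs, ECGs and laboratory tests, as one where no other explanation is likely. Section 9.1.3 defines Probable as an event that other factors could also have caused.

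**The case against.** The strongest reply is that investigators use judgement and the protocol leaves room for it. The further factors in 9.1.3 and the standard in 9.1.1 ("is at least a reasonable possibility, ie, the relationship cannot be ruled out") would let a sensible investigator call a well-timed itch possibly related. In Protocol 1.2.3 the sponsor itself says a causal link between EYP001a and transaminase rises cannot be excluded. This stands in part: the gap is strict only on a literal reading. But the further factors change no definition, and 9.1.3 says the grades follow the definitions.

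Other safeguards also stand. All SAEs (9.3) and AESIs (9.1.4) go to the safety designee within 24 hours whatever their grade. SUSAR reporting lies with the sponsor or designee, and the documents do not rest it on the investigator's grade alone. All TEAEs are tabulated by group. Section 3.2 has triggers that need no causality grade, among them CK, troponin, the Appendix E criteria, any Grade 5 toxicity, and more than 2 patients with Grade 3 or higher toxicity in one category.

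A reader might go further than the documents allow in four ways:

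- *That plausible reactions in general cannot be graded as related.* A known-type, well-timed event that improves on stopping is Definite or Probable.
- *That every unexpected reaction, and so every SUSAR, is shut out.* Section 9.1.2 includes unexpected severity; a known-type reaction of greater severity can still be graded.
- *That the gap is frequent.* The documents do not report how many events lacked dechallenge or were of a new type.
- *That rewording Possible would bring these events under the SAE criterion in 3.2.* That criterion uses only the two top grades, and 3.2 says a possible relationship does not require suspension.

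**Conclusion.** The scale is wrong as written: it is a stated rule that misgrades events when followed, not a missing detail. Two classes have no grade of Possible or higher: known type with fitting timing but no positive dechallenge, and fitting timing with a type not yet known for the drug. In the literal enumeration these are 2 + 4 = 6 of the 8 combinations with fitting timing. This measures the hole in the scale, not the share of events that fall into it.

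The exposed outputs are the drug-related TEAE and SAE tables and the investigator's causality input to SUSAR assessment, and the error runs towards understatement. This assumes that the grades are applied literally and that related means Possible or above. The second assumption cannot be checked, because neither document maps grades to related; that omission is part of the problem.

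**What to change.** 1. In Protocol 9.1.3, reword Possible to cover events whose timing is compatible with study drug and for which other causes are also plausible, requiring neither a known reaction type nor dechallenge. Keep non-fitting timing for Improbable and Not related.
2. State in Protocol 10.2.4.1 and SAP 3.7.1 which grades count as study drug-related.
3. Reconcile Protocol 3.2 with 9.1.3 on the meaning of a probable relationship and on the dependence of the SAE criterion on grades that presuppose stopping. No stopping rule is proposed here.

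The cost is moderate. Protocol 13.1 requires IRB/IEC and competent authority approval for an amendment that affects the evaluation of safety, and sites and the eCRF guidance would need a short update. Part A is already locked (Protocol 5.4) and the Part B interim was completed in February 2021 (SAP 4.1), so events graded before the change must be re-reviewed or flagged in the tables. Stating the mapping in the SAP is worthwhile even if the amendment comes too late to affect grading at sites.

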9.1.4 Adverse Events of Special Interest

The Investigator will monitor each patient for clinical and laboratory evidence for predefined AESIs throughout the patient's participation in this study.

In Part A, events of pruritus, drug-induced liver injury, and all muscle-related adverse events will be monitored as AESIs during this study; the Investigator will assess and record these events on a separate AESI form. Pruritus will be assessed using a visual analog scale and 5-D questionnaire (degree, duration, direction, disability, and distribution) itch scale at each study visit after screening. See [Appendix C](#) and [Appendix D](#).

In Part B, events of elevation of transaminases and all muscle-related adverse events will be monitored as AESIs during this study; the Investigator will assess and record these events on a separate AESI form.

During the course of the study, additional AESIs may be identified by the Sponsor; the Investigator will assess and record in detail any additional information on AESIs on an SAE form (whether or not the event meets seriousness criteria in Section 9.2), to be submitted within 24 hours of awareness of the event.

Adverse events of special interest must be recorded on the eCRF and sent to the ENYO safety designee via fax or email within 24 hours.

Safety Contact Information

PharmaLex

[contact]

[contact]

Email: [contact]

9.2 Serious Adverse Events

An adverse event or adverse reaction is considered serious if, in the view of either the Investigator or Sponsor, it results in any of the following outcomes:

- Death.
- A life-threatening adverse event.
 - Note: An adverse event or adverse reaction is considered “life-threatening” if, in view of either the Investigator or Sponsor, its occurrence places the patient at immediate risk of death. It does not include an event that, had it occurred in a more severe form, might have caused death.
- Requires hospitalization or prolongation of existing hospitalizations.
 - Note: Any hospital admission with at least 1 overnight stay will be considered an inpatient hospitalization. An emergency room or urgent care visit without hospital admission will not be recorded as an SAE under this criterion, nor will hospitalization for a procedure scheduled or planned before signing of informed consent, or elective treatment of a preexisting condition that did not worsen from baseline. However, unexpected complications and/or prolongation of hospitalization that occur during elective surgery should be recorded as adverse events and assessed for seriousness. Admission to the hospital for social or situational reasons (ie, no place to stay, live too far away to come for hospital visits, respite care) will not be considered inpatient hospitalizations.
- A persistent or significant disability/incapacity or substantial disruption of the ability to conduct normal life functions.
- A congenital anomaly/birth defect.
- An important medical event.
 - Note: Important medical events that do not meet any of the above criteria may be considered an SAE when, based upon appropriate medical judgment, they may jeopardize the patient and may require medical or surgical intervention to prevent 1 of the outcomes listed above. Examples of such medical events include allergic bronchospasm requiring intensive treatment in an emergency room or at home, blood dyscrasias or convulsions that do not result in inpatient hospitalizations, or the development of drug dependency.

9.3 Serious Adverse Event Reporting – Procedures for Investigators

Initial Reports

All SAEs occurring from the time of informed consent until 14 days following the last administration of study drug must be reported to ENYO Pharma SA (hereinafter, ENYO) and its safety designee within 24 hours of the knowledge of the occurrence.

To report the SAE, complete the SAE form electronically in the electronic data capture (EDC) system for the study and also complete and submit the SAE form to the safety vendor. When the form is completed, ENYO safety personnel and its safety designee will be notified electronically by the EDC system that an event has been added. If the event meets serious criteria and it is not possible to access the EDC system, send an email to the ENYO safety designee or call the ENYO safety designee SAE reporting line (contact information listed below), and fax/email the completed paper SAE form to the ENYO safety designee within 24 hours of awareness. When the EDC system becomes available, the SAE information must be entered within 24 hours of the system becoming available.

Follow-Up Reports

The Investigator must continue to follow the patient until the SAE has subsided or until the condition becomes chronic in nature, stabilizes (in the case of persistent impairment), or the patient dies.

Within 24 hours of receipt of follow-up information, the Investigator must update the SAE form electronically in the EDC system for the study and submit any supporting documentation (eg, patient discharge summary or autopsy reports) to the ENYO safety designee via fax or email. If it is not possible to access the EDC system, refer to the procedures outlined above for initial reporting of SAEs.

Safety Contact Information

PharmaLex

[contact]

[contact]

Email: [contact]

